#### 4.3.7 Need for additional analgesics

In the case of insufficient pain relief after two doses of IMP, additional analgesic medication may be administered at the discretion of the treating investigator, in accordance with standard local practice. The type of rescue medication, dose and time of administration will be recorded in the eCRF. If a participant is given additional analgesics during the study, the pain assessments after administration of rescue medication will not be included in the efficacy analyses. This will be further described in the statistical analysis plan.

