### Part 2; Baseline and IMP treatment (Day 1)

The baseline assessment will include a repeat pain score, sedation score, and measurement of the participant's vital signs (respiratory rate, pulse rate, oxygen saturation) if not already undertaken at

the routine triage assessment. Once the pre-treatment assessments are performed the IMP will be administered.

After administration of IMP, pain scores will be assessed at the following approximate intervals (10, 15, 20, 30, 45, 60 min post IMP), as specified in the Study Assessment Chart (Table 1). The actual timepoints for pain assessment relative to IMP administration will be recorded in the eCRF.

Unscheduled pain intensity scores will be measured and documented during any potentially painful intervention (e.g. during the application of a plaster cast for a fracture), prior to rescue medication or prior to premature study withdrawal.

Where pain relief at 10-15 min after the first IMP administration is insufficient (for example, a pain score >4/10 on NRS, or at the discretion of the treating investigator), a second IMP dose of similar strength and dose can be administered to the participant. In the case of insufficient pain relief after two doses of IMP, additional analgesic medication may be administered at the discretion of the treating investigator, in accordance with standard local practice. The medication, dose and time of administration will be recorded in the eCRF.

After administration of IMP, level of sedation, vital signs (pulse rate, peripheral oxygen saturation, respiratory rate), nasal tolerability and spontaneously reported adverse events will be assessed.

Pain scores and safety assessments should continue for 60 min after the last dose of IMP, or until additional analgesic treatment or procedures need to be initiated. For further guidance on assessments at the treatment and post-treatment visit (Part 2), see Study Assessment Chart, Table 1.

Feasibility and treatment satisfaction in relation to the IMP and route of administration will be assessed prior to ED discharge.

Treatment satisfaction will be addressed by using the following standardized question: *“How satisfied are you with the study drug that you/your child received? Please think about how it helped their pain, how it was given, any side effects, and how quickly you/your child recovered”*. Respondents will answer using a 5-point Likert scale (very unsatisfied, unsatisfied, neutral, satisfied, very satisfied).

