**Part 3; Text/telephonic follow-up for safety (Day 2-7)**

On day 2-7 the parent/legal guardian (or patient if aged 16 to <18) will be contacted via text message (if possible), asking if the patient has experienced any side effects following discharge from the ED. If the reply is “yes” or the person does not respond to the text, the site investigator will attempt to contact them by phone to obtain further information about these adverse events. A total of 3 attempts will be made to make telephone contact. If all attempts are unsuccessful, the patient’s General Practitioner (GP) may be contacted for any relevant follow-up information. For further guidance on assessments, see Study Assessment Chart in Table 1.

Table 1: Study Assessment Chart

Visit Number and Name	1 Screening	2 Baseline and IMP Treatment	3 Follow-up (phone)
Study day	1	1	2-7
Study Activities			
Signed Informed Consent	X		
Allocation of participant ID	X		
Inclusion/Exclusion Criteria	X		
Type of injury*	X		
Demographics*	X		
Relevant Medical and surgical history*	X		
Recent and Concomitant medication* g)	X	X	X
Weight*	X		
Peripheral oxygen saturation*		X	
Pulse rate*		X	
Respiratory rate*		X	
Sedation score a)		X	
Pain intensity assessment* b)	X	X	
Administration of IMP c)		X	
Adverse events/ Serious adverse events d)		X	X
Nasal tolerability e)		X	
Feasibility and Treatment satisfaction questions f)		X	

\* if data from assessments performed prior to ICF signature are part of normal ED procedure they can be used in the study.

- a) Sedation will be assessed immediately after pain intensity assessments using the UMMS score at baseline and at 10, 15, 20, 30, 45 and 60 min post-IMP. If a second dose of IMP is needed the sedation score will be performed at the same time points relative to the second dose.
- b) Pain assessment will be performed using age-appropriate scales and they will be performed at screening, at baseline (before IMP administration), and at 10, 15, 20, 30, 45, 60 min post IMP. If a second dose of IMP is needed, the pain assessment timepoints will continue for 60 min after last IMP or until additional analgesics or procedures needs to be initiated. Unscheduled pain assessments should be done during any potentially painful intervention (e.g. during the application of a plaster cast for a fracture), prior to rescue medication or prior to premature study withdrawal.

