- c) IMP will be administered to the participant while sitting in an upright position using the appropriate strength depending on the participant's weight. See more info in the IMP section and in the IMP manual.
- d) Adverse events will be collected spontaneously at all visits using open questioning.
- e) Nasal tolerability and irritation will be assessed using combined participant reported symptoms and investigator examination/inspection of the nasal cavities. Nasal tolerability will be performed twice; appr 30 min and 60 min after the *last* IMP administration (following pain, sedation and vital signs assessments).
- f) Treatment satisfaction will be addressed by asking the standardized questions "*How satisfied are you with the study drug that you/your child received? Please think about how it helped their pain, how it was given, any side effects, and how quickly you/your child recovered*". Respondents will answer using a 5-point Likert scale (very unsatisfied, unsatisfied, neutral, satisfied, very satisfied). Feasibility (i.e. acceptance of nasal administration) will be addressed by the healthcare staff asking the child: *If you were in this situation again*

and needed pain medication, would you like to receive the nasal spray? If not possible by the child, the parent/legal guardian will assess nasal acceptability.

g) Any medication given for AEs during the time from enrolment to follow up should be entered in the eCRF. Any 'rescue medication' (described as additional analgesics due to insufficient effect of IMP during the 60 min after the last dose of IMP), should be entered in the eCRF. The time given should also be noted.

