### 4.3.2 Pain intensity assessments

The pain resulting from injury causing the emergency visit will be quantified. The participant will be introduced to the age-appropriate pain scale and overall pain will be assessed, with no distinction made between spontaneous pain and any procedural pain.

Immediately prior to administration of the IMP (baseline), the pain intensity will be rated using the applicable tool (see below). Subsequent pain assessments will be performed at 10, 15, 20, 30, 45, and 60 min post IMP administration. If a second dose of IMP is administered after 10-15 min, the pain assessment schedule will be reset, and pain will be measured at 10, 15, 20, 30, 45, and 60 min after the second dose of IMP, or until additional analgesics or procedures needs to be initiated.

Unscheduled pain intensity scores will be measured and recorded during any potentially painful intervention (e.g. during the application of a plaster cast for a fracture), prior to rescue medication or prior to premature study withdrawal.

Age-appropriate pain intensity assessment tools will be used:

**Age ≥9 years:** The Numerical Rating Scale (NRS) will be used. The NRS scales consists of a Likert scale, anchored with numbers 0-10, with 0 marked "No pain" and the right end (10) marked "Worst pain imaginable". The patient will state the number representing their current level of pain, and the study staff will circle the applicable number on the CRF page (see [Appendix A](#)).

**Age ≥5 to <9 years:** The visual analogue scale modified with six faces developed by Wong-Baker (Wong-Baker FACES pain rating scale) will be used. Numerical values (0, 2, 4, 6, 8, 10) are listed for each face (Wong et al, 2001, see [Appendix B](#)).

**Age 1 to <5 years:** The study investigator will provide an assessment of pain, using the FLACC scale (Merkel et al, 1997, see [Appendix C](#)).

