### 7.3 Method of imputation

The amount of missing data will be reported as appropriate, and no other imputation will be performed.

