#### Change in pain intensity

The change in pain intensity from baseline will be computed for each subject at 10, 15, 20, 30, 45 and 60 min post IMP and this parameter will be summarized by the median and IQR and reported by age group and dose level.

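### The primary 15-minute responder rate has two conflicting clocks for children given a second dose; secondarily, dropping scores after rescue makes later change from baseline look better than it is

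*Combined protocol and SAP*

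**What the plan says.** *Redosing and the clock.* Section 4.2 (Part 2) allows a second dose 10 to 15 minutes after the first when relief is insufficient, with a score above 4 as the example and room for the investigator's discretion. Three places then describe the pain schedule:

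- Section 4.3.2: "If a second dose of IMP is administered after 10-15 min, the pain assessment schedule will be reset", followed by a new set of times counted from the second dose.
- Table 1, footnote b: "If a second dose of IMP is needed, the pain assessment timepoints will continue for 60 min after last IMP".
- Section 6.1.1: scores at 10 to 60 minutes, counted from the first dose.

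The endpoint in section 6.1.1 is a score of 4 or below at 15 minutes, and at any time within 30 minutes, after IMP. It does not name the dose. Section 4.2 adds: "The actual timepoints for pain assessment relative to IMP administration will be recorded in the eCRF".

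*Rescue and missing scores.* Section 4.3.7 states that "the pain assessments after administration of rescue medication will not be included in the efficacy analyses" and leaves further detail to the SAP. Table 1, footnote g, describes rescue as "additional analgesics due to insufficient effect of IMP during the 60 min after the last dose of IMP". Under section 4.2, scoring runs for 60 minutes after the last dose "or until additional analgesic treatment or procedures need to be initiated". Section 7.3 reads: "The amount of missing data will be reported as appropriate, and no other imputation will be performed". In section 7.4.2, change from baseline "will be computed for each subject at 10, 15, 20, 30, 45 and 60 min post IMP" and is summarised by median and IQR. The synopsis also plans means with 90% confidence intervals for change from baseline.

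*Who is analysed.* Section 7.2 puts every dosed child in the FAS and uses the FAS for the primary and secondary objectives. The synopsis promises a missing-data method for each set of efficacy endpoints. Section 7 gives none beyond 7.3.

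**The concern.** A site that follows section 4.3.2 and a site that follows section 6.1.1 will score redosed children at different times, and both will label a value as the 15-minute score. The children affected are not a random subset. The usual trigger for redosing, a score above 4, is the complement of response, so the children whose status is unclear have been selected largely on the endpoint itself. The protocol can be explicit on this: section 4.3.5 ties the nasal assessments to the last dose. The primary efficacy endpoint has no such sentence.

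The second issue concerns the later timepoints. If children leave the summary because the product did not work well enough, those who remain look better than the group that was treated. The study has one arm, so no comparator loses children in the same way.

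**Working it through.** **The plan's own figure.** Section 7.1 gives 113 children for at least 80% power, one-sided 5%, for 60% against 71.6%.

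- Normal approximation: [1.645·√(0.60×0.40) + 0.842·√(0.716×0.284)]² / 0.116² = 104.4. With continuity correction it is 112.9, so 113.
- Exact check at n = 113, requiring 77 or more responders: alpha 0.046, power 0.822.
- Dropout: 113/0.75 = 150.7, against the stated 150.

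The sample size reproduces and this point does not affect it. I use 150 as the number of children below.

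**Where the 15-minute score falls.** Under the section 4.3.2 reset, a second dose at minute *d* puts the next scheduled scores at *d*+10, *d*+15 and so on after the first dose:

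- *d* = 10: 20, 25, 30, …
- *d* = 12: 22, 27, 32, …
- *d* = 14: 24, 29, 34, …

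None includes 15 minutes after the first dose. The reset 15-minute score lies 25 to just under 30 minutes after it. A child scored at 15 minutes and redosed afterwards is unaffected.

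**Effect on the 15-minute rate.** The documents give no redosing rate, so the inputs are assumptions: *k* children redosed before 15 minutes, 80% response among the others, and 40% response among redosed children 15 minutes after the second dose.

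| *k* | Redosed counted as non-responders: 0.8(150−*k*)/150 | Last-dose clock: [0.8(150−*k*)+0.4*k*]/150 | Gap: 0.4*k*/150 |
|---|---|---|---|
| 15 | 108/150 = 72.0% | 114/150 = 76.0% | 4 points |
| 30 | 96/150 = 64.0% | 108/150 = 72.0% | 8 points |
| 45 | 84/150 = 56.0% | 102/150 = 68.0% | 12 points |

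If 20% to 60% of redosed children respond after the second dose, the last-dose figures become 74.0–78.0%, 68.0–76.0% and 62.0–74.0%. If the score 15 minutes after the first dose is actually taken, the first column is the floor, because some redosed children may have reached 4 or below by then.

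**Effect of dropping post-rescue scores.** The rescue rate is also not given. Assume non-rescued children average −4.0, which is then the reported mean, and rescued children average *m* before rescue. With rescued share *r*, the mean for all children is −4(1−*r*) + *m·r*:

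| *m* | *r* = 10% | *r* = 20% | *r* = 30% |
|---|---|---|---|
| 0 | −3.6 | −3.2 | −2.8 |
| −1 | −3.7 | −3.4 | −3.1 |
| −3 | −3.9 | −3.8 | −3.7 |

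For the planned median, take a normal mixture (non-rescued mean −4, SD 2; rescued mean −1, SD 1). The all-children medians are −3.72, −3.37 and −2.93. Rounded to whole scores they are −4, −3 and −3, against −4 in non-rescued children. The median therefore does not move at 10% rescued and moves one point at 20% and 30%.

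**Procedure stops.** With 20% of children stopped for a procedure, the all-children mean is 0.8×(−4) + 0.2*p*. This is −4.2, −4.0 or −3.8 if the stopped children average *p* = −5, −4 or −3. The direction is open.

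**The case against.** *The endpoint already has a rule.* Section 6.1.1 counts from the first dose and defines the rate as the share of participants who have a qualifying score, and section 7.2 keeps every dosed child in the analysis. Read together, a child without such a score is not a responder. This stands to the extent that the defect is a conflict between sections, not silence. It does not remove the conflict, because section 4.3.2 tells staff not to schedule the score that section 6.1.1 needs. A reader might infer that redosed children would be dropped, which would give 80% in every row and gaps of 8, 16 or 24 points. No passage says so: section 7.3 bars imputation but does not remove anyone, and sections 6.1.1 and 7.2 favour the full denominator.

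*The SAP will deal with it.* Section 4.3.7 defers detail to a separate SAP, which was not available and may answer the analysis questions. However, it need only be signed before database lock, and it cannot supply a pain score that was never taken.

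*The analysis is descriptive.* This is true, and a reader might infer from 56% against 68% that the choice of clock decides whether the trial beats 60%. Section 7.4.1 plans no such test, and the redosing shares are assumed. A descriptive proportion with a confidence interval still needs a defined numerator.

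*The late summaries are secondary, use the median, and come with counts.* This largely stands as to size. The counts and the rescue tables show the loss but do not correct the estimate. A reader might infer that the late results as a whole lean toward CT001. Only the rescue part has a known direction, because procedure stops can go either way. Nor does the point extend to AUC: section 6.1.2 gives no formula or window, so no error can be shown there.

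**Conclusion.** Two defects hold on the text.

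The main one is that sections 4.3.2 and 6.1.1 and Table 1 footnote b do not agree on the time origin of a primary endpoint. The ambiguity falls on children selected largely for not yet having responded. Between counting them as non-responders and using a last-dose clock, the 15-minute rate differs by 4, 8 or 12 points for 15, 30 or 45 of 150 children redosed before 15 minutes, given the assumed 80% and 40% response.

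The lesser one is that excluding post-rescue scores without replacement overstates later change from baseline through rescue. The mean is overstated by 0.3, 0.6 or 0.9 points at 10%, 20% or 30% rescued, if rescued children stood at −1. The median on whole scores moves by nothing at 10% and about one point at 20–30%.

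The redosing, rescue and response figures show sensitivity and are not predictions. Both defects should be fixed, but neither invalidates the design.

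**What to change.** 1. Reconcile section 4.3.2, Table 1 footnote b and section 6.1.1 to one stated time origin, and name the dose in the wording of both responder endpoints. If the origin is the first dose, keep a scheduled score 15 minutes after it for redosed children.
2. State in sections 7.3 and 7.4.1 that all FAS children form the denominator of both responder rates, and that a child rescued by 15 minutes, or without a 15-minute score, is a non-responder at 15 minutes. Add an observed-case sensitivity analysis that shows scores missing because of procedures separately.
3. For change from baseline, keep rescued children in the later summaries using the pre-rescue score that sections 4.2 and 4.3.2 already collect. Amend section 7.3 to allow this, and show observed-case results alongside. Carrying that score forward is itself an assumption, which is why both sets of results are needed.
4. Reconcile sections 4.2 and 4.3.7, which describe additional analgesia after two doses, with section 5.1.2, which allows rescue at any time. The timing of rescue determines which scores are excluded.

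The cost is wording, a few tables, possibly one added pain score in redosed children, and somewhat less favourable figures. Some scores missing because of procedures will count as failures in the main 15-minute analysis; the sensitivity analysis shows how many.

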#### 4.3.8 Demographics and weight

The bodyweight (in kg) of the participant will be measured during screening. Where a patient's injury makes weighing impractical, an estimated weight will be documented. Recording of demographics (sex, date of birth, ethnicity) will also be performed during screening.

#### 4.3.9 Adverse events

See section 6.3 Adverse Events and Serious Adverse Events.

#### 4.3.10 Concomitant medication

The following medications will be reported:

- Prescription medications within the previous 7 days.
- Over-the-counter medications within the previous 24 hours.
- IN medications within the previous 48 hours.

#### 4.3.11 Any medication given for AEs during the time from enrolment to follow up should be entered in the eCRF. Any 'rescue medication' (described as additional analgesics due to insufficient effect of IMP during the 60 min after the last dose of IMP), should be entered in the eCRF. The time given should also be noted. Feasibility / Treatment satisfaction

Feasibility / treatment satisfaction in relation to the IMP and route of administration will be assessed prior to ED discharge.

Treatment satisfaction will be addressed using the following standardized question: *"How satisfied are you with the study drug that you/your child received? Please think about how it helped their*

*pain, how it was given, any side effects, and how quickly you/your child recovered".* Respondents will answer using a 5-point Likert scale (very unsatisfied, unsatisfied, neutral, satisfied, very satisfied).

Feasibility (i.e. acceptance of nasal administration) will be addressed by the healthcare staff asking the child: *If you were in this situation again and needed pain medication, would you like to receive the nasal spray (relative to an injection, tablet or suppository for the pain)?* If not possible by the child, the parent/legal guardian will assess nasal acceptability. Answers will be "yes", "no", "I don't know". If not possible by the child, then the parent/guardian.

#### 4.3.12 Text/telephonic follow-up for safety

On day 2-7 the parent/legal guardian (or patient if aged 16 to <18 if in accordance with local legislation) will be contacted via text message, asking if the patient has experienced any side effects following discharge from the ED. If the reply is "yes" or the person does not respond to the text, the site investigator will attempt to contact them by phone to obtain further information about these adverse events. A total of 3 attempts will be made to make telephone contact. If all attempts are unsuccessful, the patient's General Practitioner (GP) may be contacted for any relevant follow-up information. The patient/ legal guardian(s) may, at any time during the study, contact the Principal Investigator, to discuss any drug experiences if needed. If it is not possible to reach the parent/legal guardian or the GP for the follow up phone call (on Day 2-7), then it should be stated that the patient is lost to follow up.

### 4.4 Participant Withdrawal

The Investigator will explain to the participant and legal guardian that they have the right to withdraw from the study at any time, and that this will not prejudice any future treatment. A participant who has consented to the study but not yet received IMP will be considered a screen failure if they decide to withdraw consent prior to receiving IMP. Once a participant has been administered IMP and subsequently decides to withdraw consent, the participant would be considered withdrawn. The reason for any kind of withdrawal must be recorded in the eCRF.

Reasons for withdrawing from may be:

- Unacceptable adverse events
- Participant or guardian's request
- Investigator's discretion
- Intercurrent illness

Whenever a participant is withdrawn from the study, the reason(s) of why the participant was withdrawn from the study should be recorded. All documentation concerning the participant must be as complete as possible, however, no new information can be collected if the participant or legal guardian has withdrawn his/her consent/assent to further study participation.

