Statistical Methods	
General principles The primary objective of this study is to investigate the safety, tolerability and analgesic effects of CT001 in pediatric participants when used in an acute care setting.
 
Data will be summarised using descriptive statistics. For continuous endpoints, the descriptive statistics include number of subjects, mean, median, standard deviation, standard error, lower and upper quartiles, minimum, and maximum. For categorical endpoints, frequency, and percentage will be given. Figures showing population distributions, such as box plots and histograms, will be reported for all applicable endpoints. The method of handling missing data for efficacy endpoints will be described for each set of endpoints. Missing data will not be imputed for safety endpoints.
 
Sample size estimation So far, data from 375 children on IN sufentanil/ketamine show a safe and tolerable combination (data from PDC 01-0201, PDC 01-0203 and PDC 01-0206). Thus, from a safety perspective it is expected that 150 patients will be sufficient to capture and confirm the adverse event profile of the IMP.
 
A formal sample size calculation was made for the primary efficacy endpoint on the basis of expecting a responder rate of 60%. A previous study reported a responder rate of 71.6 %, defined as pain intensity <math>\leq 3</math> at 30 min post IMP (16). With a sample of 113 patients, a one-sample one-sided proportion design would provide at least 80% power to show that the responder rate is more than to 60%, with a significance level of 5%. Accounting for an approximate 25% dropout rate the resulting sample size is 150.
 
Study populations The full analysis set (FAS) will consist of all patients who received at least one dose of study treatment (CT001). The FAS follows the intention-to-treat (ITT) principle, i.e. patients will be analysed regardless of whether treatment was received as planned. The FAS will be used for all analyses of primary and secondary safety and efficacy objectives.
 
The FAS will be used to tabulate demographic data, baseline disease characteristics, and subject disposition.
 
Statistical analysis of the primary endpoints The primary objective of the study will be evaluated using the FAS population. Data will further be evaluated by age group.
 
Descriptive statistics will be used for safety variables. Safety variables of special interest consist of vital signs, respiratory rate, pulse rate, oxygen saturation (SpO2), heart rate as well as sedation.
 
Clinically significant out-of-range values and clinically significant relevant changes of values will be described descriptive statistics, number of subjects, number of events.
 
Adverse events will be coded according to the MedDRA dictionary. The frequencies of adverse events will be tabulated by body system and "preferred term".

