## 4.5 Replacement of participants

In total, 150 evaluable participants will be included and exposed to IMP. If a participant/legal guardian withdraws his/ her consent prior to IMP dosing, he/ she will be replaced. If a participant is withdrawn due to technical reasons or due to a surgical unrelated medical complication, he/ she will be replaced.

Rescreening of participants will not be allowed.

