#### Enrolled population

The enrolled population consists of all enrolled participants regardless of receiving study treatment.

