#### Full Analysis Set (FAS)

The full analysis set (FAS) will consist of all participants who received at least one dose of study treatment. The FAS follows the intention-to-treat (ITT) principle, i.e. participants will be analysed, regardless of whether treatment was received as planned. The FAS will be used for the analysis of primary and secondary objectives.

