### Feasibility (Acceptance of Nasal administration)

The categorical responses 'Yes', 'No' and 'I don't know' by the child or their caregiver to the question: '*If you were in this situation again and needed pain medication, would you like to receive the nasal spray (relative to an injection, tablet or suppository for the pain)?*' will be summarised counts and percentages by age group and for all subjects. Frequency graphs may also be used to summarise the data.

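### Children who refuse the nasal spray before any dose appear neither in the acceptance percentage nor in the disposition table, so the feasibility figure describes dosed children only

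*Combined protocol and SAP*

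**What the plan says.** Section 2 lists feasibility as a secondary objective. Sections 4.3.11 and 6.2.2 equate it with acceptance of nasal administration: before ED discharge the child, or failing that the parent or guardian, is asked whether the spray would be wanted in the same situation again, compared with an injection, tablet or suppository. Under 7.4.2 the answers yes, no and I don't know "will be summarised counts and percentages by age group and for all subjects".

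On analysis sets, 7.2 defines the FAS by receipt of at least one dose and adds: "The FAS will be used for the analysis of primary and secondary objectives". The protocol outline says: "The FAS will be used to tabulate demographic data, baseline disease characteristics, and subject disposition". Section 7.2 also defines a wider set: "The enrolled population consists of all enrolled participants regardless of receiving study treatment". Section 7.4 assigns no analysis to that set.

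For children who leave before dosing, 4.4 says: "A participant who has consented to the study but not yet received IMP will be considered a screen failure if they decide to withdraw consent". Under 4.5, if the participant or legal guardian "withdraws his/ her consent prior to IMP dosing, he/ she will be replaced". The only other replacement rule reads: "If a participant is withdrawn due to technical reasons or due to a surgical unrelated medical complication, he/ she will be replaced". Failure to administer the spray is not mentioned. Section 4.4 requires the reason for any withdrawal to be recorded in the eCRF, and 3.3 has screen failures noted on a form.

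**The concern.** Refusal at the moment of administration is direct evidence on whether children accept the nasal route. Under the plan that evidence stays out of the endpoint that carries its name. Replacement then brings the number of dosed children back to target, so nothing in the reported denominator shows that anyone was lost. Because disposition is tabulated on the same set, a reader of the study report has no planned table from which to recover the count.

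Feasibility is in the study title and is likely to be quoted as a single percentage. Readers will take that percentage to describe children offered the spray, when it describes children who received it.

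**Working it through.** **Step 1. Follow three children through the rules.**

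| Child | Screen failure? | Replaced? | In FAS? | In acceptance % and disposition? |
|---|---|---|---|---|
| Refuses before any dose, consent withdrawn | Yes (4.4) | Yes (4.5) | No (7.2) | No |
| Stays consented, spray cannot be given | Not defined | Only if this counts as a technical withdrawal (4.5) | No (7.2) | No |
| Dosed, would not want the spray again | No | No | Yes | Yes, as *no* |

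The reference to all subjects in 7.4.2 does not bring the first two children back: 7.2 assigns secondary objectives to the FAS, and the question is put after treatment.

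The Enrolled population is not a ready-made remedy either. Section 3.3 enrols every eligible child once screening is complete, section 4.4 then calls an undosed child whose consent is withdrawn a screen failure, and section 7.2 keeps undosed children in the Enrolled population. The documents do not say whether the first child stays in that set.

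**Step 2. Inputs for the size.** The plan states no expected acceptance, no expected refusal and no target for this endpoint, so there is no plan figure to reproduce. (The sample-size calculation in 7.1 concerns the pain responder rate and has no bearing here.)

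- Dosed children: 150 (4.5), all assumed to answer.
- Screened: 180 (4.1), so 180 − 150 = 30 screened children beyond the 150, for all reasons together.
- Acceptance among dosed children, *a*: assumed 80%, 90% or 100%.
- Undosed refusers, *r*: assumed 0, 5, 10 or 15. The extreme value of 30 supposes that every one of the extra screened children was eligible and refused or could not receive the spray.

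**Step 3. Formula.** Counting undosed refusers as not accepting, acceptance among all who were offered the spray = *a* × 150 / (150 + *r*). At *a* = 90% the numerator is 135.

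| *r* | *a* = 80% | *a* = 90% | *a* = 100% |
|---|---|---|---|
| 0 | 80.0% | 135/150 = 90.0% | 100.0% |
| 5 | 77.4% | 135/155 = 87.1% | 96.8% |
| 10 | 75.0% | 135/160 = 84.4% | 93.8% |
| 15 | 72.7% | 135/165 = 81.8% | 90.9% |
| 30 | 66.7% | 135/180 = 75.0% | 83.3% |

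In every row the plan would report the *r* = 0 value.

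**Step 4. Smallest age group.** Section 5.4 sets a minimum of 20 children aged 1 to under 5 years. With 18 of 20 answering yes (90%), two undosed refusers give 18/22 = 81.8% and five give 18/25 = 72.0%. This shows how sensitive a small group is; it is not evidence that refusal is more common at that age.

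**The case against.** The endpoint as worded asks about a future occasion and compares the spray with other routes. It is coherent as a question for children who have experienced the product. A dosed child may answer *no* or *I don't know*, and a reluctant child who is nevertheless dosed stays in the FAS. Counting children who were never exposed as not accepting would create a different, composite endpoint. This stands, and it is why the FAS percentage should be kept and relabelled rather than replaced.

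The information is also not wholly lost. Withdrawal reasons go into the eCRF, screen failures go on a form, and the screening log in 8.3.1 needs an explanation for exclusion. Section 7 defers detail to a separate SAP, which could still assign an analysis to the Enrolled population. This stands in part: the reasons listed in 4.4 are generic (such as a request by the participant or guardian), none identifies refusal of the spray, and no planned analysis in the protocol text uses them.

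A reader might infer three stronger things that the documents do not support:

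- That children who cannot be given the spray are also screen failures and are replaced. The rule in 4.4 is tied to withdrawal of consent; for these children only exclusion from the FAS follows.
- That the percentage is a foregone conclusion because everyone in it has already accepted the spray. FAS membership means one dose received, not acceptance.
- That the bias is worst in the youngest children. No refusal rate by age is given, consent comes from a parent or guardian at that age, and the parent or guardian answers when the child cannot.

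**Conclusion.** The gap is real but narrow. For refusal before dosing with withdrawal of consent, the sequence of screen failure, replacement, exclusion from the FAS and absence from both the acceptance and disposition tables follows directly from the text. For children who stay consented but cannot be given the spray, exclusion from the FAS follows and the rest is undefined.

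The reported figure therefore measures willingness to reuse among dosed children. Read as acceptance of the nasal route, it is either unbiased or too high, provided that a child who refuses the spray is regarded as not accepting it. The size cannot be determined from the documents. At an assumed 90% among dosed children, the overstatement runs from 0 points with no refusers, through 2.9, 5.6 and 8.2 points for 5, 10 and 15 refusers, to 15.0 points in the extreme case. That last value needs the whole screening margin to be spray refusal or failed administration, although the margin must also cover ineligibility, so it is a ceiling under the planned numbers and not an expectation.

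The endpoint is secondary and descriptive, with no test or success criterion. This is a cheap improvement to what the trial can say about feasibility, and it does not threaten the primary results.

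**What to change.** 1. In the protocol outline and 7.2, tabulate disposition over all consented, eligible children instead of the FAS. Reconcile 3.3, 4.4 and the Enrolled population definition in 7.2 so that an eligible child who withdraws before dosing stays in that denominator. State how a child who remains consented but cannot be given the spray is classified and whether that child is replaced.
2. Add *refused or unable to receive nasal spray* as a recorded reason in the eCRF and on the screen-failure form.
3. In 7.4.2, report the number and percentage with that reason by age group, over all consented, eligible children, as a separate category beside the yes, no and I don't know results. Do not overwrite the answer of any child who received IMP and was asked. The documents do not define whether a part dose counts as one dose, and sprays given in the wrong number are already captured as medication errors.
4. Keep the FAS percentage, labelled *willingness to reuse among dosed children*.

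The cost is one added reason on existing forms, a few extra table rows and consistent wording across the affected sections. The feasibility result may look less favourable. If there are few or no refusals, the report will be able to show that, which it cannot do as the plan stands.
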